### 9.8.3 Safeguards, security and traceability of contacts

Operators of the call centre specialised in health surveys, will be assigned to the project and trained on the survey methodology prior to fieldwork. The emails contacts and phone calls will be traced using the management software. All survey aspects from protocol development to the reporting of the results will be conducted according to the Standard Operating Procedures (SOPs) of IMS Real World Evidence Solutions and IMS Medical Radar divisions. These SOPs can be consulted on site (14).

## 9.9 STRENGTHS AND LIMITATIONS OF THE RESEARCH METHODS

### 9.9.1 Strengths:

#### 1) use of IMS OneKey reference lists of physicians

The IMS OneKey file used to target interviewed physicians is an international database that cover more than 80 countries and 8.5 millions of HCPs/health facilities. In each country, the database is fully representative of the HCPs population.

The information contained in the file of each country is updated constantly with proactive updates. Quality controls are implemented on a regular basis.

2) The sampling of physicians follows a stratified randomised method which guarantees the representativeness of the contacted population in order to limit selection bias due to voluntary participation. Batches of physicians will be contacted up to five times before moving forward to other physicians in the lists.

3) The questionnaire includes general questions followed by specific ones in order to limit a learning process during the survey. It included both open- and closed questions. As the physicians may understand the right answer in subsequent questions, it would not be possible to go back in the questionnaire and edit answers in former questions.

The questionnaire is tested for its clarity and absence of questions raisons social desirability bias. The translation of the questionnaire is tested before implementation.

4) The study is conducted by an experienced team specialised in the design and conduct in such survey in safety area. It follows IMS SOPs (14) as well as the methodological guidelines on ENCePP and EMA GVP.

### 9.9.2 Possible selection bias due to voluntary participation

The potential for selection bias of physicians participating in a survey is an inherent bias/limitation to any study based on volunteer participation. In order to quantify any selection bias, the distribution of each stratification criterion of physicians (country and specialty) will be compared between participants and non-participants.

### 9.9.3 Limits inherent to web surveys

In such surveys, the generalisation and external validity of the results is restricted to physicians who have an active email address and willing (and able) to answer a questionnaire online. These physicians may not be fully representative of the whole targeted population (15).

Among non-response bias, targeted physicians may also have activated filters in their mail box in order to block spams and unsolicited emails. They may not even see the invitation to participate in the survey if a very strict degree of message filtering is set. Having multiple email addresses could also be a critical situation. If the one used is not the primary address or if the physicians do not check their email box frequently they will not receive the invitation during the recruitment period. Some physicians who were sent a letter may not have received it. This is one of the reasons why some physicians will also be contacted by phone.

Moreover, web surveys may promote social desirability bias which refers to the tendency of physicians to give socially desirable/expected responses instead of choosing those reflecting their current knowledge or behavior, e.g. physicians can copy-paste information gathered online instead of giving their own opinions (15).

Social desirability can affect the validity of survey research findings, but the use of pre-populated items in the questionnaire could/tends to reduce this bias (16).

The access to the web questionnaire interface will be strictly limited to the invited participants, with the possibility to participate only once and with a traceability system. Thus stakeholder bias (multiple answers of people who have a personal interest in survey results and/or who incite peers to fulfill the survey in order to influence the results) or unverified respondents (when it is not possible to verify who responds) are not applicable.

#### **9.9.4 Possible recall bias for prescription details report**

The physicians will be asked to provide prescription cases out of mind. The main reason for asking physicians to provide prescriptions details out of mind is that we wanted to keep the study pragmatically simple and within the definitions of a survey.

The collection of data through patient records would be categorised as chart review in most of the participating countries and would require Ethics Committee submissions, which is a time consuming process. This would delay the administration of the survey too far from the communication of the RMMs (DHPC and EM), which by itself would lead to a recall bias. The trade-off between a survey and a chart review was a difficult one. But, as the initial PRAC request was for a survey, and the present survey is complemented with a drug utilisation study using secondary data sources, to keep it as simple as possible.

However, this section of the survey is prone to both recall bias and selection bias. Physicians are asked to report prescription cases systematically and without omission.

Clinicians generally know and remember patients with chronic disease and long term follow-up, but in spite of the guideline of systematic selection they may select specific patients because they have a better memory of their conditions.

The results of this section will be interpreted with caution due to the likelihood of biases. However these biases would not affect the core survey questionnaire which deals with physicians' knowledge and opinions.

#### **9.9.5 Generalisation of the survey results to the overall target population with adjustment**

Since the study design presents an over-sampling mainly in Greece or Portugal, and less frequent specialties as rheumatologists or orthopedists/ orthopedic surgeons and an under-sampling in France, Italy and of GPs, the raw survey results will not be generalised to the overall target population, except if a sample adjustment is applied. For more accuracy and transparency, both unweighted (i.e. raw data) and weighted results will be presented in the report.

Since the IMS lists may identify a limited number of physicians who were not targeted with the DHPC and EM, the results may be impacted.

### **9.10 OTHER ASPECTS**

None

## 10. PROTECTION OF HUMAN SUBJECTS

The survey is non-interventional and totally anonymous to the study sponsor. Data collected will remain absolutely confidential, and only aggregated data will be analysed and communicated in a report.

### 10.1 REGULATORY AND ETHICS CONSIDERATIONS

#### 10.1.1 Ethical principles, laws and regulations

The survey will follow the regulatory and ethical requirements of each country. The survey will comply with the module VIII of the good pharmacovigilance practices (GVP).

IMS will follow the European Pharmaceutical Marketing Research Association (EphMRA) code of conduct guidelines (17) for all countries. Since the physicians will be asked to recall out of mind the prescriptions' details, no legal approvals or information are required for the four countries.

### 10.2 PHYSICIANS INFORMATION

Physicians participating in the survey will be informed about the targets of the investigation, the nature of the transmitted data, the intended use of data, recipients of these data, and their right of access and rectification to their personal data, as well as their right of objection to use their data or to IMS keeping their data.

#### 10.2.1 Physicians compensations

Physicians will be offered a compensation for the time spent participating in this survey (that they may refuse). The time to complete the survey is estimated between 10 to 15 minutes, plus an additional 5 minutes for each prescription reported (up to five prescriptions).

The amount of this compensation will be determined according to the EphMRA recommendations and the Association of Opinion and Behaviour in health field research companies (ASOCS) charter, and which states:

“When it is necessary to compensate a physician in return to the time spent during an interview or a group meeting, the compensation must not exceed the fees commonly taken by the physician for his/her advice or consultation and must be proportional to the time provided. The compensations should be clearly stated prior to the physician's participation in the survey. They must be declared to the tax authorities in accordance with applicable laws”.

### 10.3 CONFIDENTIALITY

#### 10.3.1 Patient confidentiality

The survey is non-interventional and totally anonymous to the study sponsor. Data collected will remain absolutely confidential, and only aggregated data will be communicated and analysed.

#### 10.3.2 Data confidentiality / Data security

Participating physicians will access the website (https secured site) via a secure link using a personalised login and password. This link is unique to each physician.

The answers provided will be collected in an anonymous way, only aggregated data and presented as a synthesis will be transmitted to the MAH.

Data will be recorded in a central database and tracked using an audit trail. The system will enable retrieving all introduced data at any time, and will include security elements to prevent others than authorized staff from accessing data. Each user will have a specific profile which will limit his/her use of the database. A security copy of the database and the application files will be made outside the server housing the web-based study. Security copies will be periodically made and stored outside this server. A copy of the data stored in the database will be transferred to MAHs at the end of the study.

Description of all elements of security and traceability will be available upon request.

#### **10.4 RECORD RETENTION**

The study documentation will be stored in the study master file.

The web questionnaires data will be stored on the survey database for 5 years.

### **11. MANAGEMENT AND REPORTING OF ADVERSE EVENTS/ADVERSE REACTIONS**

#### **11.1 ADVERSE EVENT COLLECTION**

The study is based on the secondary use of data. Adverse events (AE) and Adverse Drug Reactions (ADR) will not be measured.

#### **11.2 AE management and reporting**

NA

### **12. PLANS FOR DISSEMINATING AND COMMUNICATING SURVEY RESULTS**

The survey will be registered in EU-PAS register (currently the ENCePP e-register of studies) by MAHs.

The statistical results will be discussed with and approved by MAHs.

A survey report including the results of the four countries will be written in English, using MAHs or IMS Health template (which is based on the template included in the GVP module VIII) and following STROBE recommendations in MS Word format (12).

The final survey report validated by MAHs will be communicated to EMA.

## 14. ANNEXES

### Annex 1: List of stand-alone documents

Number	Document reference number	Date	Title
1-Protocol	Version 2	April 2016	Evaluation of the Effectiveness of Risk Minimisation Measures: A Joint PASS Survey among Health Care Professionals to Assess their Knowledge and Attitudes on Prescribing Conditions of Thiocolchicoside containing Medicinal Products for Systemic Use in France, Greece, Italy and Portugal
2-Questionnaire	Version 2	April 2016	Evaluation of the Effectiveness of Risk Minimisation Measures: A Joint PASS Survey among Health Care Professionals to Assess their Knowledge and Attitudes on Prescribing Conditions of Thiocolchicoside-containing Medicinal Products for Systemic Use in France, Greece, Italy and Portugal

**Annex 2: ENCePP checklist for study protocol**

## ENCePP Checklist for Study Protocols (Revision 2, amended)

Adopted by the ENCePP Steering Group on 14/01/2013

The [European Network of Centres for Pharmacoepidemiology and Pharmacovigilance \(ENCePP\)](#) welcomes innovative designs and new methods of research. This Checklist has been developed by ENCePP to stimulate consideration of important principles when designing and writing a pharmacoepidemiological or pharmacovigilance study protocol. The Checklist is intended to promote the quality of such studies, not their uniformity. The user is also referred to the [ENCePP Guide on Methodological Standards in Pharmacoepidemiology](#) which reviews and gives direct electronic access to guidance for research in pharmacoepidemiology and pharmacovigilance.

For each question of the Checklist, the investigator should indicate whether or not it has been addressed in the study protocol. If the answer is "Yes", the page number(s) of the protocol where this issue has been discussed should be specified. It is possible that some questions do not apply to a particular study (for example in the case of an innovative study design). In this case, the answer 'N/A' (Not Applicable) can be checked and the "Comments" field included for each section should be used to explain why. The "Comments" field can also be used to elaborate on a "No" answer.

This Checklist should be included as an Annex by marketing authorisation holders when submitting the protocol of a non-interventional post-authorisation safety study (PASS) to a regulatory authority (see the [Guidance on the format and content of the protocol of non-interventional post-authorisation safety studies](#)). Note, the Checklist is a supporting document and does not replace the format of the protocol for PASS as recommended in the Guidance and Module VIII of the Good pharmacovigilance practices (GVP).

### Study title:

Evaluation of the Effectiveness of Risk Minimisation Measures: A Joint PASS Survey among Health Care Professionals to Assess their Knowledge and Attitudes on Prescribing Conditions of Thiocolchicoside containing Medicinal Products for Systemic Use in France, Greece, Italy and Portugal

### Study reference number:

XXXXX

Section 1: Milestones	Yes	No	N/A	Page Number(s)
1.1 Does the protocol specify timelines for				
1.1.1 Start of data collection 				13, 14
1.1.2 End of data collection 				13, 14
1.1.3 Study progress report(s)				
1.1.4 Interim progress report(s)				
1.1.5 Registration in the EU PAS register				1
1.1.6 Final report of study results.				13, 14

### Comments:

No progress reports are planned.

 Date from which information on the first study is first recorded in the study dataset or, in the case of secondary use of data, the date from which data extraction starts.

 Date from which the analytical dataset is completely available.

Section 2: Research question	Yes	No	N/A	Page Number(s)
2.1 Does the formulation of the research question and objectives clearly explain:				
2.1.1 Why the study is conducted? (e.g. to address an important public health concern, a risk identified in the risk management plan, an emerging safety issue)				11, 15-17
2.1.2 The objective(s) of the study?				11, 18
2.1.3 The target population? (i.e. population or subgroup to whom the study results are intended to be generalised)				12, 19
2.1.4 Which formal hypothesis(-es) is (are) to be tested?				
2.1.5 If applicable, that there is no a priori hypothesis?				

Comments:

For 2.1.4 and 2.1.5: there is no formal hypothesis.

Section 3: Study design	Yes	No	N/A	Page Number(s)
3.1 Is the study design described? (e.g. cohort, case-control, randomised controlled trial, new or alternative design)				12, 19
3.2 Does the protocol specify the primary and secondary (if applicable) endpoint(s) to be investigated?				
3.3 Does the protocol describe the measure(s) of effect? (e.g. relative risk, odds ratio, deaths per 1000 person-years, absolute risk, excess risk, incidence rate ratio, hazard ratio, number needed to harm (NNH) per year)				

Comments:

For 3.2: the objectives will be answered by descriptive analysis, but no specific endpoints are defined.

Section 4: Source and study populations	Yes	No	N/A	Page Number(s)
4.1 Is the source population described?				19-20, 21
4.2 Is the planned study population defined in terms of:				
4.2.1 Study time period?				19
4.2.2 Age and sex?				19,20
4.2.3 Country of origin?				16,17
4.2.4 Disease/indication?				15
4.2.5 Co-morbidity?				
4.2.6 Seasonality?				
4.3 Does the protocol define how the study population will be sampled from the source population? (e.g. event or inclusion/exclusion criteria)				21-27

Comments:

For 4.2.5 and 4.2.6: the study population presented with painful muscle contractures.  
For 4.3, see § 9.5.1 Sampling plan p.21,22 of the protocol.

Section 5: Exposure definition and measurement	Yes	No	N/A	Page Number(s)
5.1 Does the protocol describe how exposure is defined and measured? (e.g. operational details for defining and				16-17

Section 5: Exposure definition and measurement	Yes	No	N/A	Page Number(s)
categorising exposure)				
5.2 Does the protocol discuss the validity of exposure measurement? (e.g. precision, accuracy, prospective ascertainment, exposure information recorded before the outcome occurred, use of validation sub-study)				
5.3 Is exposure classified according to time windows? (e.g. current user, former user, non-use)				19
5.4 Is exposure classified based on biological mechanism of action and taking into account the pharmacokinetics and pharmacodynamics of the drug?				
5.5 Does the protocol specify whether a dose-dependent or duration-dependent response is measured?				

Comments:

For 5.2, 5.4 and 5.5: no measurement will be done on exposure data.  
For 5.3: the time window of exposure considered is specified in the questionnaire.

Section 6: Endpoint definition and measurement	Yes	No	N/A	Page Number(s)
6.1 Does the protocol describe how the endpoints are defined and measured?				
6.2 Does the protocol discuss the validity of endpoint measurement? (e.g. precision, accuracy, sensitivity, specificity, positive predictive value, prospective or retrospective ascertainment, use of validation sub-study)				

Comments:

For 6.1 and 6.2: the survey is descriptive. No specific endpoints are defined.

Section 7: Confounders and effect modifiers	Yes	No	N/A	Page Number(s)
7.1 Does the protocol address known confounders? (e.g. collection of data on known confounders, methods of controlling for known confounders)				
7.2 Does the protocol address known effect modifiers? (e.g. collection of data on known effect modifiers, anticipated direction of effect)				

Comments:

--

Section 8: Data sources	Yes	No	N/A	Page Number(s)
8.1 Does the protocol describe the data source(s) used in the study for the ascertainment of:				
8.1.1 Exposure? (e.g. pharmacy dispensing, general practice prescribing, claims data, self-report, face-to-face interview, etc.)				21
8.1.2 Endpoints? (e.g. clinical records, laboratory markers or values, claims data, self-report, patient interview including scales and questionnaires, vital statistics, etc.)				
8.1.3 Covariates?				
8.2 Does the protocol describe the information available from the data source(s) on:				
8.2.1 Exposure? (e.g. date of dispensing, drug quantity, dose, number of days of supply prescription, daily dosage, prescriber)				21-22
8.2.2 Endpoints? (e.g. date of occurrence, multiple event,				

Section 8: Data sources	Yes	No	N/A	Page Number(s)
severity measures related to event)			×	
8.2.3 Covariates? (e.g. age, sex, clinical and drug use history, co-morbidity, co-medications, life style, etc.)			×	
8.3 Is a coding system described for:				
8.3.1 Diseases? (e.g. International Classification of Diseases (ICD)-10)				1
8.3.2 Endpoints? (e.g. Medical Dictionary for Regulatory Activities (MedDRA) for adverse events)				
8.3.3 Exposure? (e.g. WHO Drug Dictionary, Anatomical Therapeutic Chemical (ATC) Classification System)				1
8.4 Is the linkage method between data sources described? (e.g. based on a unique identifier or other)				

Comments:

For 8.1.2, 8.1.3, 8.2.2 and 8.3.2: the survey is descriptive. No specific endpoints are defined  
For 8.2.1 and 8.3: see the survey questionnaire.

Section 9: Study size and power	Yes	No	N/A	Page Number(s)
9.1 Is sample size and/or statistical power calculated?				12, 21-25

Comments:

--

Section 10: Analysis plan	Yes	No	N/A	Page Number(s)
10.1 Does the plan include measurement of excess risks?		×		
10.2 Is the choice of statistical techniques described?	×			12, 29-31
10.3 Are descriptive analyses included?	×			12, 29-31
10.4 Are stratified analyses included?	×			29-31
10.5 Does the plan describe methods for adjusting for confounding?				
10.6 Does the plan describe methods addressing effect modification?				

Comments:

--

Section 11: Data management and quality control	Yes	No	N/A	Page Number(s)
11.1 Is information provided on the management of missing data?	×			27
11.2 Does the protocol provide information on data storage? (e.g. software and IT environment, database maintenance and anti-fraud protection, archiving)	×			27,32,35
11.3 Are methods of quality assurance described?	×			31-32
11.4 Does the protocol describe possible quality issues related to the data source(s)?	×			31-32
11.5 Is there a system in place for independent review of study results?	×			32

Comments:

--

Section 12: Limitations	Yes	No	N/A	Page Number(s)
12.1 Does the protocol discuss: 12.1.1 Selection biases? 12.1.2 Information biases? (e.g. anticipated direction and magnitude of such biases, validation sub-study, use of validation and external data, analytical methods)				32-33
				32-33
12.2 Does the protocol discuss study feasibility? (e.g. sample size, anticipated exposure, duration of follow-up in a cohort study, patient recruitment)				22,31
12.3 Does the protocol address other limitations?				32-33

Comments:

--

Section 13: Ethical issues	Yes	No	N/A	Page Number(s)
13.1 Have requirements of Ethics Committee/Institutional Review Board approval been described?				34
13.2 Has any outcome of an ethical review procedure been addressed?				
13.3 Have data protection requirements been described?				34-35

Comments:

For 13.2: see section 9.9.4 p.33.
-----------------------------------

Section 14: Amendments and deviations	Yes	No	N/A	Page Number(s)
14.1 Does the protocol include a section to document future amendments and deviations?				14

Comments:

--

Section 15: Plans for communication of study results	Yes	No	N/A	Page Number(s)
15.1 Are plans described for communicating study results (e.g. to regulatory authorities)?				36
15.2 Are plans described for disseminating study results externally, including publication?				36

Comments:

--

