## 8. RESEARCH QUESTION AND OBJECTIVES

### 8.1 RESEARCH QUESTION

The research question is whether the DHPC and EM, implemented as RMMs, were effective to ensure:

- correct knowledge of physicians about prescribing conditions and safe use when prescribing systemic thicolchicoside,
- appropriate attitude when prescribing systemic thicolchicoside, in particular as concerns pregnancy, lactation and contraception.

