**Table 9.5.2–1: Sample size obtained for various precisions and proportions**

Margin of error for 95% CI				
Proportion	5%	4%	3%	2%
10%	139	216	384	864

30%	323	504	896	2,017
50%	384	600	1,067	2,401
70%	323	504	896	2,017
90%	139	216	384	864

Since the proportion of physicians informed about the updated prescribing conditions and recommendations for safe use of systemic thiocolchicoside is not known and there is no evidence supporting the expected proportion, the worst case hypothesis will be assumed considering that 50% of physicians will have received and understood the safety information distributed recently. This assumption yields the largest sample size.

Considering this hypothesis and in order to achieve a CI of 95% with a half-width of 4%, a total of 600 analysable physician questionnaires will be needed for the overall sample. Considering a margin of error of 5% (or 3% respectively) instead of 4%, the required sample size would be 384 (or 1,067) analysable physician questionnaires for the overall sample.

Based on IMS Medical Radar experience from previous similar surveys and estimates and the evaluation of the survey feasibility with four countries, the sample size of 600 is considered for this study. Indeed, the elected sample size should be sufficient to be divided between 4 countries and further between 3 groups of specialities.

It is estimated that about 30% of physicians will not complete the questionnaire until the end or not be analysable (i.e. physicians who respond to questions regarding their knowledge on the updated safety concerns of systemic thiocolchicoside or physicians without any prescription of systemic thiocolchicoside in the last 12 months or physicians who have to interrupt the interview due to an emergency (rare)). Taking into account these respondent physicians without analysable questionnaires, the overall sample size of 780 participating physicians will be required to reach 600 analysable questionnaires (i.e. recruitment of physicians should continue until 600 analysable questionnaires have been reached).

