**Table 9.7.1–1: Mock table to implement in the statistical and study reports**

Country	Question 1...				
	General practitioners	Rheumatologists	Orthopedists / orthopedic surgeons	All (unweighted)	All (weighted)
France	(N=xx)	(N=xx)	(N=xx)	(N=xx)	(N=xxx)
answer 1	xx (xx.x%)	xx (xx.x%)	xx (xx.x%)	xx (xx.x%)	xx (xx.x%)
answer 2	xx (xx.x%)	xx (xx.x%)	xx (xx.x%)	xx (xx.x%)	xx (xx.x%)
answer 3	xx (xx.x%)	xx (xx.x%)	xx (xx.x%)	xx (xx.x%)	xx (xx.x%)
Greece	(N=xx)	(N=xx)	(N=xx)	(N=xx)	(N=xx)
answer 1	xx (xx.x%)	xx (xx.x%)	xx (xx.x%)	xx (xx.x%)	xx (xx.x%)
answer 2	xx (xx.x%)	xx (xx.x%)	xx (xx.x%)	xx (xx.x%)	xx (xx.x%)
answer 3	xx (xx.x%)	xx (xx.x%)	xx (xx.x%)	xx (xx.x%)	xx (xx.x%)
Italy	(N=xx)	(N=xx)	(N=xx)	(N=xx)	(N=xx)
answer 1	xx (xx.x%)	xx (xx.x%)	xx (xx.x%)	xx (xx.x%)	xx (xx.x%)
answer 2	xx (xx.x%)	xx (xx.x%)	xx (xx.x%)	xx (xx.x%)	xx (xx.x%)
answer 3	xx (xx.x%)	xx (xx.x%)	xx (xx.x%)	xx (xx.x%)	xx (xx.x%)
Portugal	(N=xx)	(N=xx)	(N=xx)	(N=xx)	(N=xx)
answer 1	xx (xx.x%)	xx (xx.x%)	xx (xx.x%)	xx (xx.x%)	xx (xx.x%)
answer 2	xx (xx.x%)	xx (xx.x%)	xx (xx.x%)	xx (xx.x%)	xx (xx.x%)
answer 3	xx (xx.x%)	xx (xx.x%)	xx (xx.x%)	xx (xx.x%)	xx (xx.x%)
Overall - unweighted results	(N=xx)	(N=xx)	(N=xx)	(N=xx)	(N=xxx)
answer 1	xx (xx.x%)	xx (xx.x%)	xx (xx.x%)	xx (xx.x%)	xx (xx.x%)
answer 2	xx (xx.x%)	xx (xx.x%)	xx (xx.x%)	xx (xx.x%)	xx (xx.x%)
answer 3	xx (xx.x%)	xx (xx.x%)	xx (xx.x%)	xx (xx.x%)	xx (xx.x%)
Overall - weighted results	(N=xx)	(N=xx)	(N=xx)	(N=xx)	(N=xxx)
answer 1	xx (xx.x%)	xx (xx.x%)	xx (xx.x%)	xx (xx.x%)	xx (xx.x%)
answer 2	xx (xx.x%)	xx (xx.x%)	xx (xx.x%)	xx (xx.x%)	xx (xx.x%)
answer 3	xx (xx.x%)	xx (xx.x%)	xx (xx.x%)	xx (xx.x%)	xx (xx.x%)

Note: the table structure may be adjusted in the final study report.

All the analysis will be descriptive in nature and no statistical comparison will be done in this study, as it does not appear to be necessary to answer suitably the survey objectives. Besides as the DHPC and EM were already distributed to all physicians of the selected specialties, a before-after study design with comparison to baseline values is not possible, as well as a case-control study.

Continuous variables will be described by their number (of valid cases, of missing values), mean, standard deviation, and median, Q1, Q3, minimum and maximum.

Categorical variables will be described as the total number and relative percentage per category. These will be the percentage per category.

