Free text answers to open-ended questions will be categorised by theme, listed according to the frequency.

Confidence intervals of 95% will be evaluated, when relevant.

The proportions of correct and appropriate answers to selected questions asked in the questionnaire will be expressed among physicians with complete analysable web questionnaires. The endpoint will be assessed overall, by country and among subgroups of physicians' specialty.

In a first step, calculations will be performed on raw data. No projection factor will be applied to generalize the results to the entire prescribers' universe. As a consequence, the line "Overall - unweighted results" will show only the results observed on the overall sample, and will not reflect the countries' universe since this sample is not proportional to the size of IMS OneKey reference files in each country.

In a second step, the results will be weighted according to the real proportion of physicians in each specialty and country in order to accurately reflect the population that the survey seeks to measure.

For each country, the results will be reported according to the prescribers' specialty distributed proportionally to their weight within IMS OneKey reference lists.

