### 9.7.3 Questionnaire analysis

The general statistical considerations described above (§9.7.1) will be applied for quantitative and qualitative variables. The number of missing data will be indicated. Missing values are expected to be few and distributed at random. Since there is no applicable method unanimously accepted, there will be no replacement or imputation of missing data (13).

Confidence intervals of 95% will be evaluated for endpoint variables.

Physicians' answers will be analysed by subgroups of physician's specialty per country, and on the overall dataset.

For each question associated to the outcomes included in the main objective, a criterion will be calculated to separate physicians with an appropriate answer (or at least one appropriate response if the corresponding question allows multiple answers or is an open-ended question). These proportions of appropriate answers will be expressed among physicians with complete web-questionnaires.

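### The survey asks whether the measures were effective, but its headline proportion is worded three ways, has no scoring rule, and has no level that would count as effective

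*Protocol*

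**What the plan says.** Section 8.1 poses the question as a verdict: "The research question is whether the DHPC and EM, implemented as RMMs, were effective to ensure" correct knowledge and appropriate attitude among prescribers.

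The protocol describes the proportion meant to answer it in three places:

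- **Section 8.2 (Objective):** targeted physicians who understood and implemented the prescribing conditions. Five separate specific objectives follow.
- **Section 9.5.2 (Study size):** the planning value is set by "considering that 50% of physicians will have received and understood the safety information distributed recently".
- **Section 9.7.1 (Study objective):** physicians who received and understood the information and agreed to implement it, reported with a 95% Wald interval.

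The only scoring rule is in 9.7.3: "For each question associated to the outcomes included in the main objective, a criterion will be calculated to separate physicians with an appropriate answer". Where a question is open-ended or allows several answers, one appropriate response is enough.

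On endpoints the document disagrees with itself. Section 9.7.1 says "The endpoint will be assessed overall, by country and among subgroups of physicians' specialty", and 9.7.3 promises confidence intervals for endpoint variables. In Annex 2, the comment on checklist item 3.2 says "the objectives will be answered by descriptive analysis, but no specific endpoints are defined", and the comment on items 6.1 and 6.2 says "the survey is descriptive. No specific endpoints are defined".

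On inference, the checklist says "there is no formal hypothesis". Section 9.7.1 says "All the analysis will be descriptive in nature and no statistical comparison will be done in this study" and rules out a before-after design.

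**The concern.** A descriptive survey needs no hypothesis test. It does need a defined main quantity, and if it is to conclude that a measure worked, it needs something to judge that quantity against. Here there is no baseline and no comparison group, so a level stated in advance is the only thing that could turn a proportion into effective or not effective. None is stated. The 50% in 9.5.2 is a worst-case planning value, not a success level.

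The quantity itself is also open. Receiving the information, understanding it, agreeing to follow it and having followed it are different outcomes, and the three sections combine them differently. Section 9.7.3 scores questions one at a time and does not say how the scores form the headline proportion. Anyone writing the report would have to settle both the proportion and the bar with the results in hand.

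**Working it through.** **1. The plan's own figure.** Section 9.5.2 uses n = P(1−P)z²/e². With P = 0.50, z = 1.96 and e = 0.04:

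0.25 × 1.96² / 0.04² = 600.2, against the stated 600. It reproduces. The 600 fixes the width of an interval for one proportion. It carries no decision rule.

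**2. The three wordings side by side.**

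| Section | Received | Understood | Agreed to implement | Implemented |
|---|---|---|---|---|
| 8.2 | – | yes | – | yes |
| 9.5.2 | yes | yes | – | – |
| 9.7.1 | yes | yes | yes | – |

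Only understanding is common to all three. Implementation in 8.2 becomes an agreement to implement in 9.7.1 and is absent from 9.5.2.

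**3. How far the combining rule moves the result.** The questionnaire is not in the protocol, so the inputs here are assumptions: five scored items (one per specific objective in 8.2), each answered correctly by a share q.

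- Per-question headline: q.
- All five correct, independent answers: q⁵.
- All five correct, correlated answers: five latent normal variables with common correlation ρ, each counted correct below the q-quantile.
- Limits under any dependence: max(0, 5q − 4) to q.

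| q | ρ = 0 | ρ = 0.5 | ρ = 0.8 | Limits |
|---|---|---|---|---|
| 80% | 0.8⁵ = 33% | 51% | 63% | 0 to 80% |
| 90% | 0.9⁵ = 59% | 71% | 79% | 50 to 90% |

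At q = 80% the gap between the per-question figure and the all-correct figure is 47, 29 or 17 points. The planned half-width is 4 points. The gap closes only under full dependence.

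**4. What a bar would then do (illustration).** At n = 600, unweighted, the 95% Wald interval is 76.8 to 83.2% for a proportion of 80% and 29.0 to 36.5% for one of 32.8%. Against an illustrative 70% bar, the same independent answers pass question by question and fail on all-correct.

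**5. Precision of the weighted overall result.** Sections 9.5.2 and 9.7.1 say that weighting is what reflects the target population. The assumption here is that the weights come from the Table 9.5.2–2 counts (total 163,178) with the planned stratum sizes of Table 9.5.2–4. Rheumatologist counts exist only for France, so nine of the twelve strata enter, with 500 of the 600 physicians.

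Variance = p(1−p) × Σ(Wₕ²/nₕ), for a common p in every stratum.

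- French GPs: W = 90,630/163,178 = 0.555, n = 90, so W²/n = 0.003428.
- Italian GPs: W = 45,203/163,178 = 0.277, n = 90, so W²/n = 0.000853.
- The other seven strata together add about 0.00011.
- Sum = 0.00439, an effective sample size of 1/0.00439, or about 228.

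Half-width at 50%: 1.96 × √(0.25 × 0.00439) = 6.5 points. At 80%: 1.96 × √(0.16 × 0.00439) = 5.2 points. The unweighted figures at n = 600 are 4.0 and 3.2.

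**The case against.** The strongest reply is that a headline result already exists. Section 9.7.1 names one overall proportion and its interval. Section 9.5.2 says the sample is meant to represent the whole, not single countries or specialties, and 9.7.1 says the unweighted overall line does not reflect the countries' populations. A reader might infer from the checklist that no result stands above any other. The documents do not support that: the overall weighted result already ranks above subgroup and raw results.

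A reader might also infer that 8.2 requires a physician to be right on all restrictions together. It does not. It lists five separate objectives, and scoring by question fits that list. An all-correct composite is one reasonable reading of the general objective, not the only one.

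Third, estimation is a legitimate design. A statistical analysis plan that is not shown may hold scoring keys and thresholds, 9.8.2 mentions composite indicators in passing, and the checklist calls itself a supporting document. Nothing in the protocol entitles the sponsors to pick a convenient figure: section 12 says they approve the results, which is not the same thing.

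Much of this stands, and it narrows the point. It does not remove it. The headline proportion is worded inconsistently inside the protocol. The protocol does not defer the endpoint to another document but says that none is defined, while referring to one elsewhere. Section 8.1 still asks for a verdict that nothing in the plan can deliver.

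**Conclusion.** The point holds in a limited form. The protocol asks whether the measures were effective, has no baseline, comparator or stated level, words its headline proportion in three ways, gives no rule for building it from the questions, and contradicts itself on whether an endpoint exists. A verdict of effective or not effective would need a proportion and a bar chosen after the data are seen.

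The size depends on assumptions. With five items at 80% correct, the overall figure lies anywhere from 33% (independent answers) to 80% (full dependence or per-question reporting), with 51% and 63% at intermediate correlations. The number of items, the share correct and the correlation are not in the documents. The figures show that the definition matters; they do not predict the result.

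The estimates themselves are not invalid. Reported as descriptive levels of knowledge and attitude, they need no success level, though the headline proportion still needs one definition.

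**What to change.** - Use one wording of the headline proportion in 8.2, 9.5.2 and 9.7.1.
- Name the weighted overall result as the main one.
- List the questions that form it and the combining rule. All core restrictions correct is one option.
- Before data collection, or at the latest before database lock, fix the level against which its lower 95% limit is read.
- Compute that limit from the weighted variance. On the Table 9.5.2–2 counts, expect about ±6.5 points at 50% and ±5.2 at 80%, and state how strata without a rheumatologist count are weighted.
- Keep per-question, country, specialty and unweighted results descriptive.
- Correct checklist items 3.2 and 6.1 to match.

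If no level is set, reword 8.1 and the planned conclusions to estimate knowledge and attitude levels, without stating that the measures were effective.

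The cost is text and one derived variable, with no added questions. No added physicians are needed provided the wider weighted interval is accepted. The real price is that the sponsors either commit in advance to a level they may miss or give up the effectiveness claim.
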